### **Post-Treatment Adverse Event**

Post-treatment AEs are defined as any adverse event reported within the following time interval (including the lower and upper limits), which is referred to as the post-treatment period:

[End date of study drug + 28 days + 1 day; Date of study discontinuation].

The analysis of post-treatment AEs will serve as one of the secondary endpoints.

### **Serious Adverse Events (SAE)**

SAEs are defined in the protocol section 10.8.6.

### **Adverse Events of Special Interest (AESI)**

AESIs in this clinical trial are defined in the protocol section 10.8.7.

#### **11.1.1. Dictionary coding of adverse events**

AEs will be coded according to the current Medical Dictionary for Regulatory Activities (MedDRA) version and will be reported by primary system organ class (SOC) and preferred term (PT). At the end of the trial all MedDRA codes will be updated to the newest version.

---

### 11.1.2. Grading of adverse events

The toxicity grade of AEs will be graded according to the NCI-CTCAE version 5.0 of November 27, 2017 using the following definitions:

- Grade 1: Mild; asymptomatic or mild symptoms; clinical or diagnostic observations only; intervention not indicated
- Grade 2: Moderate; minimal, local or non-invasive intervention indicated; limiting age-appropriate instrumental activities of daily living (refers to preparing meals, shopping for groceries or clothes, using the telephone, managing money, etc.)
- Grade 3: Severe or medically significant but not immediately life-threatening; hospitalization or prolongation of hospitalization indicated; disabling; limiting self-care activities of daily living
- Grade 4: Life-threatening consequences; urgent intervention indicated
- Grade 5: Death related to AE

### 11.1.3. General Rules for AE reporting

#### AE tables

- All safety analyses will be done using the FAS by cohort and overall.
- AEs will be summarised by SOC and PT. The SOCs and PTs will be used for tabulation
- AE frequency tables will display the number of events (incidence), the number of subjects experiencing an event and the percentage of subjects with the event by SOC and PT
- If a subject reported more than one AE with the same PT, the AE with greatest severity and the closest association with the study drug will be presented
- If a subject reported more than one AE with the same PT, the AE with the maximum toxicity grade will be presented
- If a subject reported more than one AE within the same SOC, the subject will be counted only once with the maximum toxicity grade at the SOC level, where applicable

#### AE listings

- All AEs will be listed by subject and cohort, along with information regarding onset, start and end date, relationship to study drug, intensity, toxicity grade, action taken with study drug, treatment of event, and outcomes based on FAS.
- In the AE listings, AEs that started prior to the administration of study drug will be flagged as pre-treatment AEs. AEs that start 28 days after the last date of study drug administration will be flagged as post-treatment AEs

### 11.1.4. Adverse Event summaries and listings

#### Overall Summary of AEs

An AE summary table will be presented showing the number of events, number of subjects and the percentage of subjects in each cohort and overall having:

- TEAEs
- Post-treatment AEs
- TEAEs by maximum intensity

- 
- Post-treatment AEs by maximum intensity
  - TEAEs by maximum grade
  - Post-treatment AEs by maximum grade
  - Treatment-emergent SAEs
  - Post-treatment SAEs
  - On-treatment deaths
  - Post-treatment deaths
  - TEAEs suspected to be related to study drug
  - TEAEs suspected to be related to study drug in each intensity/toxicity grading
  - Post-treatment AEs suspected to be related to study drug
  - Post-treatment AEs suspected to be related to study drug in each intensity/toxicity grading
  - All AEs suspected to be related to study drug
  - All AEs suspected to be related to study drug in each intensity/toxicity grading
  - TEAEs leading to discontinuation of study drug
  - IRRs by grade
  - Treatment-emergent AESIs by grade
  - Post-treatment AESIs by grade

#### **TEAEs (serious and non-serious)**

The following summary tables will be provided:

TEAEs regardless of study drug relationship by primary SOC, PT and grade

Non-serious TEAEs in  $\geq 5\%$  of subjects regardless of study drug relationship by primary SOC and PT

TEAEs regardless of study drug relationship by primary SOC, PT and intensity

TEAEs regardless of study treatment relationship of  $\geq$  grade 3 by primary SOC, PT and grade.

TEAEs suspected to be related to study drug by primary SOC, PT and grade

TEAEs suspected to be related to study drug by primary SOC, PT and intensity

TEAEs suspected to be related to study drug of  $\geq$  grade 3 by primary SOC, PT and grade.

TEAEs leading to any action on study drug by primary SOC, PT and grade (any action includes: Drug withdrawn, drug interrupted)

TEAEs related to COVID-19 by primary SOC, PT and grade

#### **Post-treatment AEs (serious and non-serious)**

The following summary tables will be provided:

Post-treatment AEs regardless of study drug relationship by primary SOC, PT and grade

Post-treatment AEs regardless of study drug relationship by primary SOC, PT and intensity

Post-treatment AEs regardless of study treatment relationship of  $\geq$  grade 3 by primary SOC, PT and grade

Post-treatment AEs suspected to be related to study drug by primary SOC, PT and grade

Post-treatment AEs suspected to be related to study drug by primary SOC, PT and intensity

Post-treatment AEs suspected to be related to study drug of  $\geq$  grade 3 by primary SOC, PT and grade

#### **Treatment-emergent and post-treatment SAE**

The following summary tables will be provided:

Treatment-emergent SAEs regardless of study drug relationship by primary SOC, PT and grade  
 Treatment-emergent SAEs regardless of study drug relationship  $\geq$  grade 3 by primary SOC, PT and grade

Treatment-emergent SAEs suspected to be related to study drug by primary SOC, PT and grade  
 Treatment-emergent SAEs suspected to be related to study drug  $\geq$  grade 3 by primary SOC, PT and grade

Post-treatment SAEs regardless of study drug relationship by primary SOC, PT and grade  
 Post-treatment SAEs regardless of study drug relationship  $\geq$  grade 3 by primary SOC, PT and grade

Post-treatment SAEs suspected to be related to study drug by primary SOC, PT and grade  
 Post-treatment SAEs suspected to be related to study drug  $\geq$  grade 3 by primary SOC, PT and grade

For the final analysis, the following tables of treatment-emergent SAEs by primary SOC and PT will be produced in addition:

regardless of study treatment relationship;  
 suspected to be related to study treatment;  
 death cases.

### **Treatment-emergent and post-treatment AESIs**

The following summary tables will be provided:

- Treatment-emergent AESIs regardless of study drug relationship by primary SOC, PT and grade
- Treatment-emergent AESIs suspected to be related to study drug by primary SOC, PT and grade
- Post-treatment AESIs regardless of study drug relationship by primary SOC, PT and grade
- Post-treatment AESIs suspected to be related to study drug by primary SOC, PT and grade

### **All AEs suspected to be related to study drug (TEAEs and post-treatment AEs)**

The following summary tables will be provided:

All AEs suspected to be related to study drug by primary SOC, PT and grade  
 All AEs suspected to be related to study drug by primary SOC, PT and intensity  
 All AEs suspected to be related to study drug of  $\geq$  grade 3 by primary SOC, PT and grade  
 All SAEs suspected to be related to study drug by primary SOC, PT and grade  
 All SAEs suspected to be related to study drug  $\geq$  grade 3 by primary SOC, PT and grade  
 All AESIs suspected to be related to study drug by primary SOC, PT and grade

### **All TEAEs (irrespective of causality) and post-treatment AEs suspected to be related to study drug**

The following summary tables will be provided:

All TEAEs (irrespective of causality) and post-treatment AEs suspected to be related to study drug by primary SOC, PT and grade  
 All TEAEs (irrespective of causality) and post-treatment AEs suspected to be related to study drug by primary SOC, PT and intensity

---

All TEAEs (irrespective of causality) and post-treatment AEs suspected to be related to study drug of  $\geq$  grade 3 by primary SOC, PT and grade

### Deaths

Information on death is captured on “Adverse Events” and “Early study discontinuation” page in the eCRF.

All deaths including those that occurred on-treatment and post-treatment, will be listed along with the primary cause of death. Post-treatment deaths will be flagged in listings.

### Infusion related reactions (IRRs)

A bar chart will be generated, showing the number of infusions (e.g. 1st infusion, 2nd infusion, etc.) (x-axis) vs. the number of subjects with at least one event of SMQ “Hypersensitivity” (narrow version) (y-axis) during or in the context of this infusion. The number of subjects receiving the respective infusion will be displayed in the bar chart as well. This analysis would be useful to identify the trend of IRR over consecutive infusions.

### Special AE listings

Special AE listings for TEAEs and post-treatment AEs by cohort on FAS, displaying details of the event(s) captured on the eCRF, will be provided for:

- Serious adverse events
- AEs leading to discontinuation of study drug
- AEs of special interest
- AEs leading to death
- AEs related to Covid-19 as assessed by the investigator in the eCRF

AEs that start 28 days after the last date of study drug administration will be flagged as post-treatment AEs.

#### 11.1.5. Specific safety evaluation

Not applicable for this trial.

#### 11.1.6. General rules for specific safety evaluation

Not applicable for this trial.

#### 11.1.7. Time to onset and duration of selected AE

For TEAEs in the following categories:

AESIs

Hematological AEs (AEs pertaining to the SOC “Blood and lymphatic system disorders” and AEs pertaining to the HLGT “Haematology investigations”)

SAEs

a plot for each category will be generated by subject (y-axis) vs. time on study (months, x-axis) showing the start and end time of an AE. Ongoing AEs and grading information will be marked for each subject.

## 11.2. Definition of new abnormalities

For the evaluation of clinical laboratory results, vital sign results and ECG results the following terms are defined:

- A new abnormality will be any abnormal post baseline result for a subject whose baseline was within normal limits
- A significant worsening will be any numeric measurement that represents a change from baseline by  $\geq 25\%$  of the baseline value, in the direction away from normal (i.e., in the direction that is clinically significant)
- An outlying result for any numeric measurement will be any post administration change from baseline that meets either of the following criteria:
  - $< 25^{\text{th}}$  percentile (Q1) – 1.5 \* interquartile range
  - $> 75^{\text{th}}$  percentile (Q3) + 1.5 \* interquartile range
- An extreme value for any numeric measurement will be any post administration change from baseline that meets either of the following criteria:
  - $< 25^{\text{th}}$  percentile (Q1) – 3 \* interquartile range
  - $> 75^{\text{th}}$  percentile (Q3) + 3\* interquartile range

Q1, Q3 and the interquartile range will be calculated for each visit in summary statistics.

## 11.3. Vital signs

### 11.3.1. Vital signs variables

The Vital Signs captured in the eCRF for each subject at each visit are the following:

Weight (Screening Visit, C1D1 and C2D1 onwards)  
 Height (only Screening Visit)  
 Systolic Blood Pressure (all visits)  
 Diastolic Blood Pressure (all visits)  
 Heart Rate (all visits)  
 Body Temperature (all visits)

### 11.3.2. Vital signs analysis

The following information will be summarized by cohort on FAS:

- Absolute values and percentage changes from baseline for all time points available
- Number (%) of subjects with at least one post-baseline abnormal value below or above the normal limit by vital signs variables
- Number (%) of subjects with at least one post-baseline significant worsening by vital sign variables
- Number (%) of subjects with at least one post-baseline outlying value by vital sign variables
- Number (%) of subjects with at least one post-baseline extreme value by vital sign variables

Normal limits are defined as follows:

Systolic blood pressure: 90-120 mmHg  
 Diastolic blood pressure: 60-80 mmHg

Heart rate: 60-100 beats per minute  
Body temperature:  
35.9-37.1 °C axillary temperature  
35.9-37.5 °C oral, ear, forehead, rectal temperature

All collected data on vital signs will be listed by visit. Each abnormal value will be flagged to show whether it is a value below or above the normal limit and whether the value is a significant worsening, an outlying value or an extreme value as defined in section 11.2.

#### **11.4. Physical examination**

At Screening, End of Treatment and End of Study full physical examinations will be performed. Limited physical examinations will include at least vital signs and general appearance. If clinically indicated, a full PE must be performed. New and worsening clinically relevant abnormal physical examination findings during the study will be entered as AEs and analysed within the AE tables. Physical examination summaries and listings will be presented for each cohort on FAS.

The number (%) of subjects at screening, EOT visit, EOS visit and any visit with a full physical examination assessment by body system of the following categories:

Normal  
Abnormal, clinically relevant  
Abnormal, not clinically relevant

For all other visits, the number (%) of subjects with abnormal findings (clinically relevant or not clinically relevant) by body system and cohort will be displayed.

Listings on individual full and limited physical examination will be presented by visit and cohort, including the assessments and description of the abnormalities.

#### **11.5. Electrocardiogram (ECG)**

ECG recordings will be obtained by a standard 12-lead ECG.

##### **11.5.1. ECG variables**

The Electrocardiogram variables captured in the eCRF for each subject at each visit are the following:

- QRS Interval
- RR Interval
- PR Interval
- QT Interval
- Heart Rate

In addition to the QT interval, QTc corrections will be calculated as follows

$$\text{Bazett's Correction (QTcB) (5): } QTcB = \frac{QT_{msec}}{\sqrt{RR}}$$

$$\text{Friderica's Correction (QTcF) (6): } QTcF = \frac{QT_{msec}}{\sqrt[3]{RR}}$$

Where relative rate (RR) = 60/heart rate.

### 11.5.2. ECG analysis

The following information will be summarized by cohort on FAS:

- Absolute values and percentage changes from baseline for all time points
- Number (%) of subjects with at least one post-baseline abnormal value below or above the normal limit by ECG variables
- Number (%) of subjects with at least one post-baseline significant worsening by ECG variables, as defined in section 11.2
- Number (%) of subjects with at least one post-baseline outlying value by ECG variables, as defined in section 11.2
- Number (%) of subjects with at least one post-baseline extreme value by ECG variables, as defined in section 11.2
- Number (%) of subjects at each time point with an ECG assessment of the following categories
  - Normal
  - Abnormal, clinically relevant
  - Abnormal, not clinically relevant
- Number (%) of subjects at each time point experienced a QTcF change from baseline of
  - < 30 ms
  - ≥ 30 ms and < 60 ms
  - ≥ 60 ms
- Number (%) of subjects at each time point experienced a QTcF prolongation of
  - QTcF: ≤ 450 ms
  - QTcF: > 450 ms and ≤ 480 ms
  - QTcF: > 480 ms and ≤ 500 ms
  - QTcF: > 500 ms

Normal limits are defined as follows:

PR interval: 120-200 ms  
 QRS interval: 80-100 ms  
 RR interval: 600-1200 ms  
 QT interval: 400-440 ms

All individual ECG data will be listed by visit and cohort, including the assessments and description of abnormalities. Each abnormal value will be flagged to show whether it is a value below or above the normal limit and whether the value is a significant worsening, an outlying value or an extreme value as defined in section 11.2.

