### 12.12.5. Electrocardiograms

Summary ECG assessment (categories: 'normal'; 'abnormal', 'clinically significant'; 'abnormal', 'not clinically significant') will be tabulated by time point using frequency tabulations.

Each result of the 12-lead ECG (PR, QRS, RR and QT interval values) will be flagged to show whether it is a value below or above the normal limit.

Summary statistics for all time points will be displayed for QT and both QTc correction methods. The Bazett's correction method for QTc (Bazett 1920) will be applied as follows:

$$\text{Bazett's Correction (QTcB)} = \text{QT/RR}^{12}$$

The Fridericia correction method for QTc (Fridericia 1920) will be applied as follows:

$$\text{Fridericia's Correction (QTcF)} = \text{QT/RR}^{13}$$

where relative rate (RR) = 60/heart rate

Also, the number and percentage of subjects with QTc values above the normal limit ( $\geq 450$  ms,  $\geq 480$  ms,  $\geq 500$  ms) and the number and percentage of subjects who experienced a change  $\geq 30$  ms or a change  $\geq 60$  ms will be presented by time point.

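### The fixed 400-440 ms normal range for uncorrected QT makes the QT row of the ECG abnormality table and the QT listing flags disagree with the SAP's own QTcF classes

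*SAP*

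**What the plan says.** SAP 11.5.1 captures QRS, RR, PR, QT and heart rate from the ECG, then adds: "In addition to the QT interval, QTc corrections will be calculated as follows". QT is therefore the uncorrected interval, and QTcB and QTcF are derived from it. For the corrections the SAP states "Where relative rate (RR) = 60/heart rate".

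SAP 11.5.2 gives normal limits for PR, QRS, RR and QT. Two of them are "QT interval: 400-440 ms" and "RR interval: 600-1200 ms". It gives no such limit for QTcF, QTcB or the ECG heart rate. The limits drive two outputs:

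- a table: "Number (%) of subjects with at least one post-baseline abnormal value below or above the normal limit by ECG variables"
- the listings: "Each abnormal value will be flagged to show whether it is a value below or above the normal limit"

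They also decide new-abnormality status. SAP 11.2 and Protocol 12.12.2 define this as an abnormal post-baseline result after a baseline within normal limits. Protocol 12.12.2 has such subjects noted in listings and reviewed by the sponsor.

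SAP 11.5.2 separately classifies QTcF as ≤450, >450 to ≤480, >480 to ≤500 and >500 ms, and QTcF change as <30, 30 to <60 and ≥60 ms. SAP 11.3.2 sets, for vital signs, "Heart rate: 60-100 beats per minute".

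Protocol 12.12.5 requires the QT value itself to be flagged as below or above the normal limit, but gives no QT limit. It also asks for "the number and percentage of subjects with QTc values above the normal limit", with cuts at ≥450, ≥480 and ≥500 ms.

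**The concern.** QT shortens as heart rate rises, which is why the SAP corrects it. A fixed 40 ms window on the uncorrected value therefore sorts tracings partly by heart rate. A long QTc at a fast rate can fall inside the window, and an unremarkable QTc can fall below it at an ordinary rate or above it at a slow one.

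The QT row could then show few subjects above the limit while the QTcF table in the same section shows prolongation. It could also show many subjects below the limit for no reason except heart rate. The sponsor's review of new abnormalities would inherit both errors. The RR and heart-rate ranges raise a smaller question of the same kind, because they do not describe the same rates.

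**Working it through.** **Inputs.** QT limits 400 and 440 ms, RR limits 600 and 1200 ms, and QTcF cuts 450, 480 and 500 ms (SAP 11.5.2). Heart-rate limits 60 and 100 bpm (SAP 11.3.2). Formula from SAP 11.5.1: QTcF = QT / RR^(1/3), with RR = 60/HR in seconds. The plan states no figure of its own to reproduce.

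**Step 1. Put the two QT limits through the formula.** For example, at 100 bpm RR = 0.6 s, and 440 / 0.6^(1/3) = 521.7 ms. The last column is the raw QT that corresponds to QTcF 450 ms, that is 450 × RR^(1/3).

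| HR (bpm) | RR (ms) | QTcF at QT 400 | QTcF at QT 440 | QT at QTcF 450 |
|---|---|---|---|---|
| 50 | 1200 | 376.4 | 414.1 | 478.2 |
| 60 | 1000 | 400.0 | 440.0 | 450.0 |
| 70 | 857 | 421.1 | 463.2 | 427.5 |
| 75 | 800 | 430.9 | 474.0 | 417.7 |
| 80 | 750 | 440.3 | 484.3 | 408.9 |
| 90 | 667 | 457.9 | 503.7 | 393.1 |
| 100 | 600 | 474.3 | 521.7 | 379.5 |

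The two scales coincide only at 60 bpm. Over the SAP's RR range, the raw QT equal to QTcF 450 ms moves by 478.2 − 379.5 = 98.7 ms. No fixed 40 ms window can follow it.

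**Step 2. Find the rate at which each limit crosses a cut.** Solve RR = (QT/cut)^3 and HR = 60/RR.

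- QT 400, cut 450: RR = (400/450)^3 = 0.7023 s, so 85.4 bpm. Above that rate the whole window has QTcF above 450 ms.
- QT 440, cut 450: RR = 0.9348 s, so 64.2 bpm.
- QT 440, cut 480: RR = 0.7703 s, so 77.9 bpm.
- QT 440, cut 500: RR = 0.6815 s, so 88.0 bpm.

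**Step 3. Check the opposite error.**

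- At 75 bpm, QT 390 ms gives 390 / 0.8^(1/3) = 420.1 ms. It is flagged low but lies in the SAP's lowest QTcF class.
- At 50 bpm (RR 1200 ms, inside the SAP's RR range), QT 441 to 478 ms is flagged high with QTcF from 415 to 450 ms.

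**Step 4. New-abnormality status.**

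- QT 405 ms at 70 bpm (QTcF 426) followed by QT 390 ms at 80 bpm (QTcF 429) counts as a new abnormality, although QTcF changed by about 3 ms.
- QT 440 ms at 60 bpm (QTcF 440) followed by QT 440 ms at 100 bpm (QTcF 522) does not count.

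**Step 5. RR against heart rate.** 60/1.2 = 50 bpm and 60/0.6 = 100 bpm, so the RR range means 50-100 bpm against 60-100 bpm for vital signs. A rate of 55 bpm (RR 1091 ms) is normal by one and low by the other.

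**The case against.** The strongest reply is that SAP 11.5.2 already handles prolongation by better means. The QTcF class and change tables do not use the 400-440 ms range, and the tracing with QT 440 ms at 100 bpm would appear there as QTcF above 500 ms. The overall normal/abnormal assessment is tabulated too, from ECGs read at the site (Protocol 10.8.3), independently of these limits. This stands. A reader might infer that prolonged QT would go unreported, and the documents do not support that.

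Four further limits on the point also stand:

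- A reader might infer that the whole ECG abnormality table is wrong. The table is by variable, and the PR and QRS rows are untouched. SAP 11.5.2 also plans no count of new abnormalities; that status matters for the listings and the sponsor's review.
- A reader might link this to the primary endpoint. That endpoint is treatment-emergent adverse events, not ECG reference flags. Protocol Table 2 schedules only two post-baseline ECGs (after dosing on C1D1, and at EOT).
- QT and QTcF are different quantities, so the two rules do not contradict each other outright. The conflict is in effect: they sort the same tracing differently.
- Neither document gives a lower QTcF limit. A QTcF of 420 ms can be called unprolonged, in the lowest class, but the documents do not define it as normal on the low side.

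Protocol 12.12.5 also requires a QT flag, so simply deleting the QT range would leave that requirement unmet. None of this rescues a fixed window on uncorrected QT as a criterion of abnormality.

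**Conclusion.** The point holds for the raw-QT row of the below/above-limit table, the QT listing flags and the new-abnormality status of QT. There the SAP's rule misclassifies in both directions at heart rates that the SAP itself calls normal: a QTcF of up to 522 ms passes at 100 bpm, and a QTcF of 420 ms is flagged low at 75 bpm.

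This rests only on the SAP's own formula, classes and ranges, taking prolonged to mean QTcF above 450 ms. How many subjects would be misclassified cannot be estimated, because the documents give no distribution of QT or heart rate in this population. The outputs are descriptive, and neither a hypothesis test nor the sample size depends on them. The correction is worth making because it is cheap and because the sponsor's safety review reads these flags.

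The RR and heart-rate ranges do disagree at the slow end. A reader might infer that the RR range should be narrowed to match, but the documents do not show which of the two should yield.

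**What to change.** In SAP 11.5.2:

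1. Add QTcF to the variables that carry a normal limit. Base the prolongation count, the listing flag and new-abnormality status on the SAP's own 450 ms QTcF cut. State whether a lower QTcF limit applies, since none is given.
2. Stop using 400-440 ms as a rate-independent criterion. Because Protocol 12.12.5 requires QT to be flagged, either keep a QT flag that accounts for heart rate (for example, raw QT against 450 × RR^(1/3)) or describe the change and its reason as a deviation from the protocol analysis, as Protocol 12.7 provides.
3. Reconcile the boundaries. A QTc of exactly 450 ms is above normal in Protocol 12.12.5 and in the lowest class in SAP 11.5.2. The same ≥ against > difference occurs at 480 and 500 ms.
4. Reconcile the RR range (50-100 bpm) with the heart-rate range (60-100 bpm), and say which limit applies to the heart rate captured on the ECG.

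The cost is SAP wording and a small change to the ECG table and listing programs. No new data are needed.
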